	
This study also aims to assess serious adverse events (SAEs), pregnancy, and infant outcomes in female participants with PNH exposed to crovalimab during pregnancy and through breastfeeding.
 
The primary objectives for this study are as follows:
 
• To characterize and estimate the frequency of adverse events of special interest among participants with PNH exposed to crovalimab. AESIs are as follows:
○ Serious infections○ Meningococcal infection and other infections with encapsulated bacteria○ Development or worsening of any neurological condition (e.g., axonal neuropathy, multifocal mononeuropathy)○ Malignancies and hematologic abnormalities○ Serious hemolysis○ Transient immune complex reactions○ Infusion and injection-related reactions• To characterize and estimate the frequency of adverse events (AEs), SAEs, pregnancy outcomes, and infant outcomes in participants with PNH exposed to crovalimab during pregnancy and through breastfeeding. Specifically:
○ To estimate the frequency and further characterize all AEs, adverse pregnancy outcomes, and birth outcomes (during pregnancy and until date of delivery), in pregnant female participants with PNH.○ To estimate the frequency and further characterize adverse fetal/neonatal/infant outcomes (e.g., major, and minor congenital malformations, gestational age, postnatal growth and development) and all AEs at birth, and through at least the first year of life of infants of mothers exposed to crovalimab during pregnancy.○ To estimate the frequency and further characterize all AEs for lactating females and
--	---

	
infants exposed to crovalimab through breastfeeding.
 
The secondary objectives for this study are as follows:
 
 • To estimate the frequency and further characterize AEs and SAEs (not included as adverse events of special interest) in all participants with PNH exposed to crovalimab. • To characterize clinical outcomes and laboratory test results relevant to PNH among participants with PNH who experienced an AESI. • To characterize patient-reported outcomes among participants with PNH who experienced an AESI via a patient-reported fatigue assessment using the Functional Assessment of Chronic Illness Therapy (FACIT)-Fatigue questionnaire.

Table 2	Probability to Observe at least one Event for AESIs with Varying Prevalence.....	37

LIST OF FIGURES

Figure 1	Schematic Representation of the Primary Data Collection in the Crovalimab Silo Registry, a Product-Specific Registry of the Core Registry.....	22
Figure 2	Study Design for PNH in the Crovalimab Silo.....	23
Figure 3	Identification of Prospective Data in The Silo Registry for Pregnancy and Infant Outcomes.....	26

2.

LIST OF ABBREVIATIONS

Abbreviation	Definition
ACOG	American College of Obstetricians and Gynecologists
AE	adverse event
AESI	adverse event of special interest
BTH	breakthrough hemolysis
CDC	Centers for Disease Control and Prevention
CSR	Clinical Study Report
DTDC	drug-target drug complexes
ECG	electrocardiogram
eCRF	electronic Case Report Form
EDC	electronic data capture
EMA	European Medicines Agency
DOC	Date of conception
FACIT	Functional Assessment of Chronic Illness Therapy
FDA	[U.S.] Food and Drug Administration
FTT	failure to thrive
GPP	Guidelines for Good Pharmacoepidemiological Practice
HDA	high disease activity
HSCT	hematopoietic stem cell transplantation
IEC	Independent Ethics Committee
IPIG	International PNH Interest Group
IR	incidence rate
IRB	Institutional Review Board
IRR	Infusion and injection related reaction
ISPE	International Society of Pharmacoepidemiology
IV	intravenous
LDH	lactate dehydrogenase
LLT	lowest level term
mAb	monoclonal antibody
MAH	Marketing Authorization Holder
MAVE	major adverse vascular event
MedDRA®	Medical Dictionary for Regulatory Activities
NIS	non-interventional study

PASS	post-authorization safety study
PIGA	phosphatidylinositol glycan class A
PNH	paroxysmal nocturnal hemoglobinuria
PPROM	preterm prelabor rupture of membrane
PRO	patient-reported outcome
QoL	quality of life
SAE	serious adverse event
SAP	Statistical analysis plan
SC	subcutaneous
SDU	secondary data use
SOC	standard of care
TICR	transient immune complex reaction
ULN	upper limit of normal
WHO	World Health Organization

4. ABSTRACT/SYNOPSIS

TITLE: A POST-AUTHORIZATION SAFETY STUDY (PASS) TO CHARACTERIZE SAFETY EVENTS AND SPECIAL CONDITIONS, SUCH AS PREGNANCY AND INFANT OUTCOMES, IN PAROXYSMAL NOCTURNAL HEMOGLOBINURIA (PNH) PATIENTS TREATED WITH CROVALIMAB WITHIN THE IPIG REGISTRY

PROTOCOL NUMBER: MO45473

VERSION NUMBER: 3.0

DATE OF SYNOPSIS: 19 June 2025

EU PAS REGISTER NUMBER: To be registered

STUDIED MEDICINAL PRODUCT: Crovalimab

SCIENTIFIC RESPONSIBLE [REDACTED]
[REDACTED]
F. Hoffman-La Roche AG

MAIN AUTHOR [REDACTED]
[REDACTED]
R. Hoffmann-La Roche AG

PHASE: IV, non-interventional study

INDICATION: Paroxysmal nocturnal hemoglobinuria

MARKETING AUTHORIZATION HOLDER: Roche Registration GmbH
[name]

RATIONALE AND BACKGROUND

Paroxysmal nocturnal hemoglobinuria (PNH) is a rare, acquired, chronic, life-threatening blood disorder associated with anemia due to hemolysis. Although there have been reports of spontaneous remission, the course of the disease is generally chronically progressive. The goal of PNH therapy is to control complement-mediated hemolysis and thus counteracting anemia. The disorder requires life-long treatment.

PNH appears to equally affect males and females, although there may be a slight female preponderance (NORD 2024). Although patients can develop PNH at any age, the typical age of presentation is between 30 and 40 years. Children can be diagnosed with PNH, though PNH diagnosis predominantly occurs during adolescence (Curran et al. 2012; Shah and Bhatt 2023). Pregnancy-related complications are also apparent in PNH, including worsening cytopenia,

Crovalimab—F. Hoffmann-La Roche Ltd
Protocol MO45473, Version 3.0

thrombosis, infections, bleeding, miscarriages, and increased maternal mortality; as well as adverse fetal outcomes of fetal death and premature delivery (Alashkar et al. 2020).

The current standard of care (SOC) for PNH involves complement inhibition, which has significantly improved patient outcomes. In countries where complement inhibitors are not currently available, management of patients is mainly through supportive care (Cançado et al. 2021).

Crovalimab, a novel, long-acting monoclonal antibody (mAb) targeting C5, has demonstrated efficacy in reducing hemolysis, improving quality of life (QoL), and potentially offers a more convenient dosing schedule compared to existing therapies. However, as crovalimab is a new treatment, comprehensive post-marketing surveillance is essential to fully understand its long-term safety profile and potential risks.

The European Medicines Agency (EMA) and the U.S. Food and Drug Administration (FDA) have requested additional data on specific crovalimab safety concerns, including:

- Serious infections
- Meningococcal infections
- Hemolysis after discontinuation
- Malignancies and hematologic abnormalities
- Transient immune complex reactions (TICRs)
- Infusion and injection-related reactions (IRRs)
- Pregnancy and infant outcomes
- Use in pregnancy and/or breastfeeding

To gather more information on the safety profile of crovalimab in a real-world setting, Roche has entered a partnership with the International PNH Interest Group (IPIG), to participate in the existing registry (further referred to as the “Core Registry”, ClinicalTrials.gov ID NCT06524726). A crovalimab sub-registry (further referred to as the “Crovalimab Silo” or Study MO44987) will be established, to enable additional safety data collection in participants with PNH treated with crovalimab. The study described herein (MO45473) is a secondary data use (SDU) study which aims to analyze data from the participants enrolled in the Crovalimab Silo.

RESEARCH QUESTION AND OBJECTIVES

The aim of this study is to characterize the safety profile of crovalimab in participants with PNH, with a specific focus on adverse events of special interest (AESIs). This study also aims to assess adverse events (AEs), serious adverse events (SAEs), pregnancy, and infant outcomes in female participants with PNH exposed to crovalimab during pregnancy and through breastfeeding.

The primary objectives for this study are as follows:

- To characterize and estimate the frequency of AESIs among participants with PNH exposed to crovalimab. Adverse events of special interest are as follows:
 - Serious infections
 - Meningococcal infection and other infections with encapsulated bacteria
 - Development or worsening of any neurological condition (e.g., axonal neuropathy, multifocal mononeuropathy)
 - Malignancies and hematologic abnormalities
 - Serious hemolysis
 - TICRs
 - Infusion and injection-related reactions
- To characterize and estimate the frequency of AEs, SAEs, pregnancy outcomes, and infant outcomes in participants with PNH exposed to crovalimab during pregnancy and through breastfeeding. Specifically:
 - To estimate the frequency and further characterize all AEs, adverse pregnancy outcomes, and birth outcomes (during pregnancy and until date of delivery), in pregnant female participants with PNH.
 - To estimate the frequency and further characterize adverse fetal/neonatal/infant outcomes (e.g., major and minor congenital malformations, gestational age, postnatal growth and development) and SAEs at birth and through at least the first year of life of infants of mothers exposed to crovalimab during pregnancy.
 - To estimate the frequency and further characterize all AEs for lactating females and infants exposed to crovalimab through breastfeeding.

The secondary objectives for this study are as follows:

- To estimate the frequency and further characterize AEs and SAEs (not included as AESIs) in all participants with PNH exposed to crovalimab.
- To characterize clinical outcomes and laboratory test results relevant to PNH disease among participants with PNH who experienced an AESI.
- To characterize patient-reported outcomes (PROs) among participants with PNH who experienced an AESI via a patient-reported fatigue assessment using the Functional Assessment of Chronic Illness Therapy (FACIT)-Fatigue questionnaire.

STUDY DESIGN

This study is a multi-center, multi-country, non-interventional, registry-based post-authorization safety study (PASS) using secondary data collected as part of the Crovalimab Silo registry (Study MO44987) of participants with PNH exposed to crovalimab, including pregnant women and their infants.

Product-specific silos initiated by the IPIG can be created on request by the respective Marketing Authorization Holders (MAHs) and will include participants treated with PNH-specific therapy from a single MAH. These silos will be established to collect specific data on treated participants with PNH and address research objectives, which are treatment-related, and/or requests from regulatory authorities. The Crovalimab Silo is a product-specific registry enrolling participants with PNH treated with crovalimab.

Participants enrolled in the Core Registry are expected to sign an Informed Consent Form for the purposes of that study. Following crovalimab treatment initiation, a separate privacy notice will be provided to the study participants, which will explain in more detail how their data will be used, the specific data processing purposes, as well as the applicable legal bases for processing the data. Participants should acknowledge and receive the privacy notice to be part of the Crovalimab Silo.

The Crovalimab Silo will encompass retrospective and prospective data from all enrolled participants with PNH treated with crovalimab, including data from female pregnant participants with PNH and their infants. Participant demographics and medical history data will be collected at enrollment. Both prospective and retrospective data will cover participants' characteristics and clinical outcomes (including safety data, pregnancy, infant outcomes, and breastfeeding), and crovalimab exposure.

Prospective data collection will commence at the initiation of treatment for participants with PNH who began therapy with crovalimab on or after the start of the Crovalimab Silo registry. For participants with PNH who began treatment with crovalimab before the Crovalimab Silo was established, retrospective data will be collected from the Core Registry into the silo, if available, while prospective data collection will begin from the time of silo enrollment.

Participants' visit schedules will follow standard of care. Participants' data are expected to be entered in the electronic data capture (EDC) system by the clinicians and/or their qualified designee at the time of registry enrollment and approximately every 6 months thereafter. In addition, participants with PNH and/or their parents/legally authorized representatives have the option to complete electronic patient-reported outcome (ePRO) questionnaires (i.e., the FACIT-Fatigue questionnaire) at registry enrollment, and every 6 months thereafter.

POPULATION

This study will include all participants with PNH who are treated with crovalimab and have available data from the Crovalimab Silo, including participants with PNH who are pregnant and information from their infants.

VARIABLES

VARIABLES FOR ALL PARTICIPANTS WITH PNH

The primary variables for all participants with PNH enrolled in this study are as follows (described as adverse events of special interest [AESIs]):

- Serious infections

Crovalimab—F. Hoffmann-La Roche Ltd
Protocol MO45473, Version 3.0

- Meningococcal infections and other infections with encapsulated bacteria
- Development or worsening of any neurological condition
- Malignancies and hematologic abnormalities
- Serious hemolysis
- Transient immune complex reaction
- Infusion- and injection-related reactions

The secondary variables for all participants with PNH this study are as follows:

- All other adverse events and SAEs (not including an AESI)
- Clinical outcomes and laboratory test results relevant to PNH among participants with PNH who experienced an AESI

One PRO instrument (the FACIT-Fatigue questionnaire) will also be used during this study.

VARIABLES FOR PARTICIPANTS WITH PNH WHO ARE PREGNANT OR BREASTFEEDING AND THEIR INFANTS

The primary variables for participants with PNH who are pregnant and their infants in this study are as follows:

- Ectopic pregnancy
- Spontaneous abortion
- Pregnancy terminations (with or without presence of fetal defects)
- Fetal death or stillbirth (with or without fetal defects)
- Live birth (with or without congenital anomaly)
- Preterm birth
- Size for gestational age
- Low birth weight
- Postnatal growth deficiency or failure to thrive (FTT)
- Infant developmental deficiency
- Congenital malformations
- Serious and severe infections and hospitalization of infants
- Neonatal death
- Perinatal death
- Infant death
- Preeclampsia
- Eclampsia
- Preterm Prelabor Rupture of Membrane (PPROM)

Crovalimab—F. Hoffmann-La Roche Ltd
Protocol MO45473, Version 3.0

- Maternal death
- Any adverse events during pregnancy
- Any adverse events for lactating females and infants through breastfeeding
- Any adverse event experienced by the infant

BASELINE AND FOLLOW-UP VARIABLES

The following baseline and follow-up variables will be collected at enrollment for all participants with PNH, during pregnancy and infant birth:

- Patient characteristics and demographics
- Clinical history relevant to PNH, including previous PNH treatment, and date of last administration
- Any concomitant medication
- Vaccination
- Breastfeeding status
- Potential confounding factors affecting safety, pregnancy, and infant outcomes

DATA SOURCES

This study will analyze data collected from the Crovalimab Silo registry.

STUDY SIZE

Enrollment depends on the approval timelines, uptake, and treatment course in each country where the sites are open, as well as the total number of evaluable participants with PNH for AESIs. However, based on patient projections in selected countries, the MAH expects 300 participants with PNH to be enrolled with up to 7 years of follow-up during the duration of the Crovalimab Silo registry (7 years).

The IPIG aims to enroll approximately 25 participants with PNH who are pregnant in the Crovalimab Silo registry. Nevertheless, since the management of PNH during pregnancy has been challenging and pregnancy has been discouraged in participants with PNH, there are very few reported cases of pregnant participants with PNH treated with C5 inhibitors. For example, in a similar registry there were only 94 pregnancies in fewer than 1,086 females treated with eculizumab from June 2006 to November 2014 (Kelly et al. 2015; Höchsmann et al. 2022).

DATA ANALYSIS

No formal statistical testing will be performed. Descriptive statistics will be reported using summary tables and figures (where appropriate). Continuous variables will be summarized using mean, standard deviation, median, range (min–max) and interquartile range. Categorical variables will be summarized using counts and proportions (%).

Additionally, incidence and incidence rate (IRs; in person-years) and their 95% CIs of AESIs, SAEs and AEs will be calculated. The exact 95% CIs will be computed using the

Crovalimab—F. Hoffmann-La Roche Ltd
Protocol MO45473, Version 3.0

Clopper-Pearson method (Clopper and Pearson 1934). For the calculation of IRs, the denominator will be the pooled person-time of all the participants within the cohort. The patient time-at-risk will be calculated from index date until the date of an incident event or censoring, whichever occurs first. All first events occurring during follow-up period will be counted in the total number of events (thus, for each participant, only the first event will be counted) and divided by the total patient-years at risk. In addition to IRs, incidence proportions will be calculated as proportion of participants afflicted with each of the AESIs, SAEs, and AEs up to the data extraction date.

Subgroup and sensitivity analyses will be implemented when sample size allows.

Analyses will be presented separately for the entire PNH participant cohort, pregnant female participants with PNH, all infants, and infants categorized by breastfeeding status (yes/no). When feasible, these analyses will be further detailed according to each trimester of pregnancy and each quarter within the infant's first year of development. Additionally, where data allows, outcomes will be analyzed based on prior PNH treatment and using the classifications of naïve new users and prevalent new users.

Potential confounding factors influencing safety and pregnancy outcomes, such as demographic information (e.g., age, race/ethnicity), clinical characteristics, maternal medical history, obstetrical history, comorbidities, and concomitant medications will be used in subgroup analyses among participants with PNH who experience an AESI, as well as for pregnancy or infant outcomes. Adverse events of special interest proportions and incidence rates will be compared between subgroups. Similarly, subgroup analysis by clinical and laboratory test outcomes for PNH will be performed when feasible. Safety events will be also described by causality.

Sensitivity analysis will be performed restricting the data to safety events and crovalimab exposure that was collected prospectively only. The effects of the timing of crovalimab exposure before and during pregnancy and cumulative exposure periods on each outcome will be also evaluated as sensitivity analysis. Sensitivity analysis may also include timing variations of failure to thrive (FTT) and development deficiency outcomes, when available.

Full details on all statistical analyses, including other subgroup and sensitivity analyses, will be described in the Statistical Analysis Plan (SAP).

MILESTONES

FIRST DATA EXTRACTION:

The date of first data extraction is the date when the variables used for the data analysis as per protocol are extracted for the first time. The planned first data extraction is after 6 months of Crovalimab Silo inception. The planned first data extraction is in Q1 2026.

LAST DATA EXTRACTION:

The last data extraction is the date of the end of the Crovalimab Silo registry, plus an additional 6 months to account for final data transfer. The planned last data extraction is in Q2 2032.

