9.7.2 Subgroup and Sensitivity Analyses

Subgroup and sensitivity analyses will be implemented when sample size allows.

Analyses will be presented separately for all participants with PNH, for pregnant female participants with PNH, for all infants, and for infants sub-grouped by breastfeeding status (yes/no).

When feasible, analyses will be further detailed according to each trimester of pregnancy and each quarter within the infant's first year of development.

To account for previous complement inhibitor exposure, subgroup analyses will be also based on previous PNH treatment exposure, using the following definitions: "naïve new users" when individuals initiate crovalimab without prior exposure to C5 inhibitors, and "Prevalent new users" when individuals initiate crovalimab after having received at least one C5 inhibitor any time prior to crovalimab treatment start. Safety events will be also described by causality.

Potential confounding factors influencing safety and pregnancy outcomes, such as demographic information (e.g., age, race/ethnicity), clinical characteristics, maternal medical history, obstetrical history, comorbidities, and concomitant medications will be described among participants with PNH who experience an AESI, as well as for pregnancy or infant outcomes. If needed, subgroup analysis will be performed and AESIs proportions and incidence rates will be compared between subgroups.

Similarly, subgroup analysis may include clinical and laboratory test outcomes for PNH (e.g., MAVEs, HDA, BTH, etc.) and previous PNH treatment.

Sensitivity analysis will be performed restricting the data to safety events and crovalimab exposure that was collected prospectively only. The effects of the timing of crovalimab exposure before and during pregnancy and cumulative exposure periods on each outcome will be also evaluated as sensitivity analysis. Sensitivity analysis may also include timing variations of FTT and development deficiency outcomes, when available.

Full details on all statistical analyses, including other subgroup and sensitivity analyses, will be described in the Statistical Analysis Plan (SAP).

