9.9.3 Confounding

Confounding arises when treatment effects or disease exposures vary due to another factor. This can be managed using stratification or subgroup analyses in the statistical evaluation.

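### The synopsis places the confounder subgroup comparison of AESI frequency among participants who already have an AESI, in conflict with section 9.7.2 and the protocol's own rate denominator

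*Protocol*

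**What the plan says.** Two places in the protocol describe the same analysis.

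- **Section 4 (synopsis), Data Analysis.** Potential confounders "will be used in subgroup analyses among participants with PNH who experience an AESI", and likewise for pregnancy and infant outcomes. The sentence that follows reads: "Adverse events of special interest proportions and incidence rates will be compared between subgroups". No other population is named between the two.
- **Section 9.7.2.** The same factors "will be described among participants with PNH who experience an AESI, as well as for pregnancy or infant outcomes". The comparison is a separate sentence: "If needed, subgroup analysis will be performed and AESIs proportions and incidence rates will be compared between subgroups". It does not limit the comparison to AESI cases.

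Both places also make subgroup and sensitivity analyses in general depend on sufficient sample size.

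The measures being compared are defined in the synopsis and again in section 9.7.1. For proportions, "incidence proportions will be calculated as proportion of participants afflicted with each of the AESIs, SAEs, and AEs up to the data extraction date". For incidence rates, the denominator is the person-time of everyone in the cohort, counted from index date to first event or censoring.

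Section 9.9.3 says of confounding: "This can be managed using stratification or subgroup analyses in the statistical evaluation".

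**The concern.** A comparison of event frequency between subgroups is informative only if each subgroup contains both participants with the event and participants without it. The population named in the synopsis contains only participants with an AESI. An analyst who follows it cannot learn whether AESI risk differs by age, comorbidity, concomitant medication or any other factor.

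This matters because the study has no comparator arm (section 9.9.8) and the protocol names stratification and subgroup analysis as its means of handling confounding. The synopsis and section 9.7.2 also give the author of the SAP two different instructions: form subgroups of cases and compare them, or describe the cases and, where needed, compare subgroups without that restriction.

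**Working it through.** The protocol gives no figure for this point, so there is nothing to reproduce. The check is of the denominator, followed by an illustration of size.

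**1. The two texts side by side**

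| | Synopsis | Section 9.7.2 |
|---|---|---|
| Role of the factors among AESI cases | used to form subgroups | described |
| Population of the comparison | AESI cases, on a literal reading | no restriction stated |
| Condition | sample size allows | sample size allows, and need |

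**2. Proportion with any AESI.** Among participants selected for having an AESI, numerator equals denominator. The result is 100% in every subgroup, whatever the true risks.

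**3. Proportion with one AESI type.** Within the same set this is P(type) / P(any AESI), which is generally below 100%. Inputs from section 9.5: serious infection 6%, injection-related reaction 6.4%, TICR 17.8%. Their overlap is not reported, so it is assumed and ranged:

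- Full overlap: P(any) = 17.8%; 300 × 0.178 = 53.4 participants.
- Independence: P(any) = 1 − 0.94 × 0.936 × 0.822 = 27.7%; about 83 participants.
- No overlap: P(any) = 6 + 6.4 + 17.8 = 30.2%; 300 × 0.302 = 90.6 participants.

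| Type | Whole cohort | Among cases, full overlap | Among cases, independence | Among cases, no overlap |
|---|---|---|---|---|
| Serious infection | 6% | 33.7% | 21.7% | 19.9% |
| Injection-related reaction | 6.4% | 36.0% | 23.1% | 21.2% |
| TICR | 17.8% | 100% | 64.3% | 58.9% |

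The columns for cases are shares of the case mix. They do not estimate the proportion that the protocol defines. For example, if types do not overlap and a factor doubles the risk of each one, every share is 2p / (2 × sum) = p / sum, unchanged.

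**4. Incidence rates.** For illustration, assume two subgroups of 150, true any-AESI risks of 10% and 30% over 5 years, and a constant hazard h = −ln(1 − risk) / 5.

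- Whole cohort: h = 0.1054 / 5 and 0.3567 / 5, that is 2.11 and 7.13 per 100 person-years.
- Cases only: the rate is 1 / (mean time to event given an event by year 5), where that mean is 1/h − 5(1 − risk)/risk. It equals 47.46 − 45.00 = 2.46 years and 14.02 − 11.67 = 2.35 years, which gives 40.7 and 42.5 per 100 person-years.

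A threefold difference in risk appears as 100% against 100%, and as two nearly equal rates.

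**5. Participants removed.** 300 minus 53 to 91 is about 209 to 247, all of them participants without one of these three events.

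**The case against.** The best case for the protocol is that the synopsis has merged two sentences of section 9.7.2, and that nobody would run the comparison among cases. The comparison sentence in the synopsis names no restricted population, the rate denominator is fixed as the whole cohort, and full details of subgroup analyses are deferred to the SAP. This makes it likely that section 9.7.2 reflects the intent. It does not remove the problem: the synopsis names a population, and that population makes the stated comparison uninformative.

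Some stronger readings are tempting, and the text does not support them.

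- A reader might infer that every AESI proportion would be 100%. That holds for any AESI, or for one type among cases of that same type. The protocol has seven AESI categories and defines proportions for each.
- A reader might infer that section 9.7.2 has the same defect. It does not restrict the comparison to cases.
- A reader might infer that one place commits to the analysis without condition. Both depend on sample size; section 9.7.2 adds only the condition of need.
- A reader might infer from section 9.9.3 that this analysis is the sole control of confounding. That section speaks of stratification or subgroup analyses in general, and the split into naïve and prevalent new users carries no AESI restriction.

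**Conclusion.** The synopsis states the wrong population for the confounder subgroup comparison. If followed, the comparison could not show whether AESI risk differs by any factor, and it contradicts section 9.7.2 and the whole-cohort person-time denominator.

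The figure of about 53 to 91 of 300 participants left rests on three trial frequencies carried over to the registry, with overlap assumed from full to none. It leaves out the other AESI categories and the longer registry follow-up, both of which could raise the number of cases. It also depends on how many participants switch from another C5 inhibitor, since section 7 says TICR affects only those who switch. The 10% and 30% risks are invented to show the mechanism. The logical point needs none of these numbers.

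The consequence is limited to a descriptive subgroup analysis. The primary frequency estimates, study size and data collection are untouched.

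**What to change.** Rewrite the synopsis sentences to match section 9.7.2:

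- Describe potential confounders among participants with an AESI, as a summary of cases.
- Compare AESI proportions and incidence rates between subgroups formed by baseline factors in all participants with PNH. For pregnancy and infant outcomes, form the subgroups in all pregnancies or all infants.
- Use one condition for the comparison, either sufficient sample size or need, worded identically in the synopsis and section 9.7.2.

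Naming the population in section 9.7.2 as well would be a useful clarification, since that section leaves it unstated. The cost is a sentence or two in each place, with no new data and no change to any primary analysis.
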